### (3) Nonclinical Study Results and Clinical Results

#### 1) Nonclinical Study Results

##### (a) Pharmacology Studies

Two non-GLP immunogenicity studies in rabbits were conducted as studies supporting the efficacy of BK1310. In Immunogenicity Study 1, the animals received BK1310 (the 10 µg formulation) by subcutaneous injection 3 times (doses of 5, 10, or 20 µg) at 2-week intervals. In Immunogenicity Study 2, the animals received BK1310 (the 5 µg and 10 µg formulations) by subcutaneous injection 3 times (doses of 5 or 10 µg PRP) at 2-week intervals. In addition, for each of the active ingredients of DPT-IPV, which is contained in BK1310, studies were conducted in accordance with the criteria stipulated in the Japanese Biological Drug Product Standards, Adsorbed-Purified Pertussis/Diphtheria/Tetanus/Inactivated Polio (Sabin strain) Combined Vaccine, Small Lot Product Tests, Potency Tests.

The results showed that, in rabbits, the administration of BK1310 resulted in an increase in the level of anti-PRP antibodies, and that combination did not result in an interference effects in the anti-PRP antibody concentration obtained.

In addition, the active ingredients contained in the DPT-IPV vaccine in BK1310 conform to the specifications listed in the Japanese Biological Drug Product Standards, and combination was not found to result in any interference effects.

##### (b) Safety Pharmacology Studies

The effects on the central nervous system, cardiovascular system, and respiratory system were evaluated in BK1310 safety pharmacology studies. Rats were used to assess the effects on the central nervous system, and monkeys were used to assess the effects on the cardiovascular and respiratory systems. The 10 µg formulation of BK1310 was used in all of these studies. The rats received doses of 0.5 mL (10 µg PRP, the same as the dose used in clinical studies), and the monkeys received 5 mL (100 µg PRP, a dose 10-fold that used in clinical studies). The animals in all of the studies received single subcutaneous doses.

It was found as a result of these studies that BK1310 (the 10 µg formulation) did not affect the animals' general symptoms or behavior observations, or any of the respiratory system parameters (respiration rate, tidal volume, respiratory minute volume) or the cardiovascular system parameters (blood pressure, heart rate, ECG) that were measured using a telemetry system.

It was therefore concluded that BK1310 does not have any effects on the central nervous system, cardiovascular system, or respiratory system.

##### (c) Toxicity Studies

Single subcutaneous dose and repeated subcutaneous dose toxicity studies were conducted in rats as BK1310 toxicity studies. In each of these studies, the 10 µg formulation of BK1310 was used, the dose was 0.5 mL/body (10 µg PRP, the same as the dose used in the clinical studies), and the animals received either single subcutaneous doses or 5 (repeated) doses at 1-week intervals at the same administration site.

No systemic or administration site toxicities attributed to BK1310 were observed in the single subcutaneous

dose toxicity studies, and it was therefore determined that the approximate lethal dose of BK1310 under these test conditions is greater than 0.5 mL/body.

Although administration site induration and changes in some of the white blood cell fractions and some of the globulin fractions were observed in the repeated subcutaneous dose toxicity studies, all of these were immune reactions to BK1310, which contains aluminum, and none were toxicologically significant. The aforementioned changes were seen to around the same extent in both the BK1310 group and the group that received the control substance (DPT-IPV), and no clear differences were found in the recoverability of these changes, either. The NOAEL of BK1310 under these test conditions exceeded 0.5 mL/body, and it was concluded that the local irritation with BK1310 was comparable to that with DPT-IPV.

## 2) Clinical Study Results

No clinical studies of BK1310 have been conducted to date.

For further details, refer to the most recent version of the BK1310 investigator's brochure.

## (4) Plans for This Study

The introduction of a DPT-IPV-Hib pentavalent vaccine would make it possible to simultaneously, in one product, confer basic immunity against pertussis, diphtheria, tetanus, polio, and Hib. This would be advantageous from the standpoint of alleviating the burden placed on infants by injections as well as reducing the burden associated with drug management. The purpose of this study is to develop BK1310, which is a pentavalent vaccine that combines MT-2301, which is an influenza b conjugate vaccine that is being developed in Japan, with TETRABIK, which is a DPT-IPV combined vaccine. This study has been designed to confirm safety and immunogenicity against Hib antigen in Cohort 1 in order to confirm the safety and efficacy of BK1310 in the clinical setting. The subsequent cohort, Cohort 2, has been designed to verify the noninferiority of BK1310 to the control, which is simultaneous vaccination with ActHIB® and TETRABIK.

Based on an investigation that took into account the results that had been obtained for the anti-diphtheria antibody titer in Cohort 1, the design was subsequently changed so that Cohort 2 would be an exploratory study in which simultaneous vaccination with ActHIB® and TETRABIK in the primary immunization is used as the control. Additionally, Cohort 3 was established so that the (sub)investigator could measure the antibody titer following the booster immunization in subjects completing Cohort 2, depending on the results obtained after the primary immunization in Cohort 2, or the subject's (legal guardian's) request.

## 2. Study Objectives

To investigate on an exploratory basis the safety of BK1310 and its immunogenicity against Hib in healthy infants, and to then investigate on an exploratory basis the efficacy and safety of BK1310 using simultaneous vaccination with ActHIB® and TETRABIK as the control.

### 3. Subjects

#### 3.1 Subjects

Healthy infants with age  $\geq 2$  months and  $< 43$  months (recommended age in months:  $\geq 2$  months and  $< 7$  months)

#### 3.2 Inclusion Criteria

Subjects meeting all of the following inclusion criteria at the time of the first vaccination with the investigational product will be eligible for study participation.

- (1) Healthy infants aged  $\geq 2$  months and  $< 43$  months (recommended  $\geq 2$  months and  $< 7$  months) at the time of the first vaccination with the investigational product. However, although persons meeting the following definition of “persons who should receive a vaccination with care” may participate in the study, whether or not to enroll them in the study should be decided carefully.
- (2) Persons from whose legal guardians written consent to study participation has been obtained.

#### Persons Who Should Receive A Vaccination With Care

- 1) Persons who clearly have underlying diseases, such as cardiovascular disease, kidney disease, liver disease, blood disease, respiratory disease, or a developmental disorder
- 2) Persons who have developed a pyrexia within 2 days after receiving a vaccination in the past
- 3) Persons with a past history of convulsions

#### Persons Who Should Receive A Vaccination With Care

The persons who should receive a vaccination with care, as defined in 1) through 3) above, were established in accordance with the Immunization Act Enforcement Regulations and the Immunization Guidelines.

- (2) The legal guardians are defined as the parents, in accordance with the “Guidance on Clinical Studies of Drug Products in Pediatric Populations” (PFSB/ELD Notification No. 1334, dated December 15, 2000).

#### 3.3 Exclusion Criteria

Subjects meeting any of the following exclusion criteria at the time of the first vaccination with the investigational product will be excluded from study participation.

- (1) Persons who have received diagnoses of immunodeficiencies in the past, or who are currently receiving treatments that cause immunosuppression
- (2) Persons with close relatives (up to third degree of kinship) who have a congenital immunodeficiency
- (3) Persons who might experience a serious allergy in response to a food, drug product, etc.
- (4) Persons who have had Hib infections, pertussis, diphtheria, tetanus, or acute poliomyelitis in the past
- (5) Persons who have received a vaccination against Hib, pertussis, diphtheria, tetanus, or polio in the past
- (6) Persons who have received live vaccines within 27 days, or inactivated vaccines/toxoids within 6 days, before the first vaccination with the investigational product
- (7) Persons who have received blood transfusions, immunosuppressants (except for topical drugs), or immunoglobulin preparations (including HB immunoglobulin preparations and monoclonal antibodies [e.g., Synagis, palivizumab])
- (8) Persons who have received corticosteroids (except for topical drugs) at a prednisolone dose level equivalent of 2 mg/kg/day or higher
- (9) Persons who have participated in another clinical study and received another investigational product within 12 weeks before obtaining informed consent
- (10) Persons who were less than 37 weeks old at birth, or who weighed less than 2500 g at birth
- (11) Persons otherwise judged to be unsuitable for participation in this study by the (sub)investigator

*Rationale*

- (1)(2)(4)(5)(7)(8) These criteria were established because these conditions could affect efficacy and safety.
- (3) This criterion was established with safety in mind, and in accordance with the Immunization Act Enforcement Regulations and the Routine Immunization Guidelines.
- (6) This criterion was established in accordance with the vaccination interval in the Routine Immunization Guidelines.
- (9) This criterion was established to ensure that this study is conducted ethically, and also because the effects on efficacy and safety of drugs that have not been properly evaluated are unpredictable.
- (10)(11) These criteria were established to ensure that this study is conducted safely and ethically.

### 3.4 Vaccination Postponement Criteria

- (1) If the subject clearly has a pyrexia (if the patient's temperature is  $\geq 37.5^{\circ}\text{C}$  immediately before vaccination)
- (2) If the subject has clearly developed a severe, acute illness
- (3) If the (sub)investigator determines for some other reasons that it would not be appropriate for the subject to receive a vaccination

*Rationale*

These criteria were established in accordance with the Immunization Act Enforcement Regulations and the Routine Immunization Guidelines.

## 4. Explanation and Consent

### 4.1 Preparation of Subject Explanation Sheet and Informed Consent Form

The principal investigator will prepare an explanation sheet for legal guardians and informed consent form (explanation sheet/informed consent form). The explanation sheet/informed consent form will be prepared as a single, unified document, and will be revised as needed.

The prepared or revised explanation sheet/informed consent form will be submitted to the study sponsor and approved by the institutional review board prior to the start of the study.

### 4.2 Information That Should be Included in the Explanation Sheet

The explanation sheet must include the following information at a minimum.

- (1) The fact that the study has an experimental aspect
- (2) The objectives of the study
- (3) The names, job titles, and contact information for the principal investigators and subinvestigators
- (4) Study method (including the experimental aspects of the study, the subject inclusion criteria and, if randomization is being performed, the probabilities of the patient being assigned to each treatment)
- (5) The expected clinical risks and benefits (If there are no expected benefits to the subject, then this must be explained to the legal guardians.)
- (6) Whether or not there are other preventive therapies that are available to the subjects
- (7) The planned term of participation in the study
- (8) The fact that participation in the study is entirely up to the legal guardian, and that the legal guardian may refuse to participate in the study or withdraw from the study at any time, and that the subject will not be subject to any discriminatory treatment because of the legal guardian's refusal to participate in or withdrawal from the study, nor will not participating in the study cause the subject to lose any benefits that the subject would have been expected to receive.
- (9) The fact that the monitors, auditors, institutional review board, and regulatory authorities will be able to access the subject's medical records (source documents), and that in the case of said access the subject's privacy will be protected Also, the fact that by affixing his or her sign or sealing on the informed consent form the legal guardian consents to said access
- (10) The fact that the subject's privacy will be protected even if the results of the study are published
- (11) Whom the legal guardian should contact at the study site if the legal guardian wants to obtain information about the study or the subject's rights or to report any health injury that is related to the study
- (12) The compensation and treatment that the subject will be able to receive if the subject suffers any health injury related to the study
- (13) Information about the types of institutional review boards that will review, for example, the appropriateness of this study, what issues will be reviewed by each institutional review board, and other information about the institutional review boards that are involved in this study
- (14) The planned sample size for the study
- (15) The fact that the legal guardian will be notified promptly if any information that could affect the legal guardian's willingness to continue participating in the study
- (16) The conditions or reasons that would cause the subject's participation in the study to be discontinued

- (17) If participating in the study will impose any financial burden on the legal guardian, the exact nature thereof
- (18) If the legal guardian will receive any financial compensation for participating in the study, the exact nature thereof (e.g., agreement on how the payments will be calculated)
- (19) The rules the legal guardian will be expected to follow

#### 4.3 Method of Obtaining Consent

Because the subjects of this study are infants, written consent will be obtained not from the subjects themselves but from the subjects' legal guardians. A legal guardian is defined as the person with parental rights for the subject in question (i.e., the father or mother).

- (1) Before initiating the study, the (sub)investigator will provide the legal guardian with an explanation sheet/informed consent form that has been approved by the institutional review board and explain its contents thoroughly to the legal guardian. A clinical research coordinator may also provide a supplemental explanation. The (sub)investigator will provide the explanation based on the explanation sheet using as simple language as possible to make sure that the legal guardian understands, and must provide adequate responses to the legal guardian's questions. The (sub)investigator will confirm that the legal guardian has thoroughly understood the explanation before obtaining the legal guardian's written consent to have the subject participate voluntarily in the study.
- (2) The (sub)investigator who provides the explanation and the legal guardian will affix their own names and seals or signatures on the consent form, and also date it. If a clinical research coordinator provides a supplementary explanation, that clinical research coordinator will also affix his or her sign or seal on the document and date it.
- (3) The (sub)investigator will, before the subject starts participating in the study, provide the explanation sheet/informed consent form with the names, seals or signatures, and dates to the legal guardian and store the original informed consent form properly, in accordance with the rules of the study site.
- (4) The date of the first informed consent obtainment will be recorded on the case report form.

#### 4.4 Informed Consent Form/Subject Explanation Sheet Revision

- (1) If new, important information is obtained that could pertain to the legal guardian's consent, the (sub)investigator will promptly convey this information orally to the legal guardian and check whether or not the subject will continue participating in the study, and will record the results in the subjects' medical records.
- (2) The principal investigator will promptly determine based on this information whether or not the explanation sheet/informed consent form needs to be revised.
- (3) If the principal investigator determines that the explanation sheet/informed consent form needs to be revised, the principal investigator will do so promptly, and must then once again have it approved by the institutional review board.
- (4) The (sub)investigator will provide the legal guardian with an explanation using the explanation sheet/informed consent form that has been newly approved by the institutional review board, and will obtain the legal guardian's written consent to voluntarily continue having the subject participate in the study.
- (5) Similar to when consent is initially obtained, the (sub)investigator who provided the explanation and the legal guardian will affix their signs or seals on the revised explanation sheet/informed consent form, and date it. If a clinical research coordinator provides a supplementary explanation, that clinical research coordinator will also affix his or her sign or seal on the document and date it.

- (6) The (sub)investigator will provide the legal guardian the explanation sheet/informed consent form with the names, seals or signatures, and dates, and will retain the original of the informed consent form properly, in accordance with the rules of the study site.

## 5. Study Design

### 5.1 Study Phase and Type

Phase of the study: 3

Type of study: Exploratory

[figure not shown]
### 5.2 Study Design

#### 5.2.1 Study Design

The study population will consist of the 3 cohorts described below (Cohort 1, Cohort 2, and Cohort 3).

##### (1) Cohort 1

A randomized, double-blind, parallel-group, multicenter study

Subjects randomized to the following groups will receive the following investigational products.

- BK1310 H group: Formulation H, 0.5 mL per dose
- BK1310 L group: Formulation L, 0.5 mL per dose

[figure not shown]
For the primary immunization, subjects will receive 3 doses of investigational product subcutaneously (upper arm extensor), 0.5 mL for each dose, at intervals of 3 to 8 weeks (standard vaccination interval: 4 weeks). For the booster immunization, subjects will receive a single dose of investigational product subcutaneously (upper arm extensor) at 6 to 13 months after the primary immunization. However, the repeated vaccination with investigational product at the same location as that which was used for the previous dose will be avoided.

Once the assessments have been performed following the first vaccination with the investigational product

to the last subject in Cohort 1 (after the primary immunization), and after the measurement of the antibody titer against Hib antigen (the anti-PRP antibody concentration) has been completed (at the time point shown in the figure above (\*)), the blind will be broken, and the BK1310 safety information will be assessed, and once it has been confirmed that the subject has been afforded adequate immunity against Hib antigen, a decision about whether or not to initiate Cohort 2 will be made based on the criteria described in “5.2.2 Cohort 2 Initiation Criteria.” Additionally, except for the study sponsor, for whom the study will not be blinded after unblinding (except for the monitors, as described in “25.1.6 Monitors”), the study will continue with the double blind maintained even after unblinding.

(2) Cohort 2

A randomized, observer-blinded, active-controlled, parallel-group, multicenter study

[figure not shown]
Subjects randomized to the following groups will receive the following investigational products. Furthermore, for BK1310 H and L groups, to which group each subject will be assigned will be decided after the completion of Cohort 1 and before the start of Cohort 2.

- BK1310 H and L groups: Subjects will receive 0.5 mL per dose of formulation H or L
- Control group: Subjects will receive 0.5 mL of each of ActHIB® and TETRABIK

For the primary immunization,\* subjects will receive 3 doses of investigational product subcutaneously (as a rule, administered at the top part of the upper arm extensor) at intervals of 3 to 8 weeks (standard vaccination interval: 4 weeks). Subjects in the control group will receive 3 doses of TETRABIK and ActHIB® subcutaneously (as a rule, administered at the top and bottom, respectively, of the upper arm extensor on the same side). However, the repeated vaccination with investigational product at the same location as that which was used for the previous dose will be avoided.

\*: The completion of the primary immunization series with the investigational product. For the booster immunization, a dose will be administered as part of, for example, routine immunization.

(3) Cohort 3

For subjects from whom written informed consent has been obtained only, and after the end of Cohort 2, and generally for 4 or more weeks after the administration of the booster immunization as part of, for example, routine immunization, the (sub)investigator will perform antibody titer measurements as a follow-up investigation, depending on the results obtained after the primary immunization in Cohort 2, or in accordance with the wishes of the subject (subject's legal guardian).

*Rationale*

Because there is no experience with the use of BK1310 in infants, this design was selected in order to confirm, on an exploratory basis, the safety and immunogenicity against the Hib antigen of BK1310 before advancing to Cohort 2, in which a large number of subjects will receive a vaccination with the investigational product. As far as the Hib antigen level of the investigational product is concerned, because the results of the Japanese phase 2 clinical study of MT-2301 revealed that efficacy and safety were comparable to those achieved with ActHIB®, both in the 5 µg group and in the 10 µg group, 2 dose levels, 5 µg (the L group) and 10 µg (the H group), as the level of polysaccharide, were selected for the level of Hib antigen of the investigational product for use in Cohort 1 as well. Additionally, for Cohort 2, in order to verify noninferiority with respect to simultaneous immunization with ActHIB® and TETRABIK in the antibody seroprotection rate following vaccination with 3 doses of BK1310 against each of the antigens contained in BK1310, the study was initiated as an active-controlled, parallel-group, multicenter study. Subsequently, the decision was made to change the study from being a confirmatory study, its initial design, to being an exploratory study with a group that would receive a vaccination simultaneously with ActHIB® and TETRABIK as a control, because of the results that were obtained in Cohort 1 for the anti-diphtheria antibody titer after the primary immunization. Furthermore, it was decided that the exploratory comparison versus the control in Cohort 2 would be performed up until Visit 4 because it was thought that this could be done using an investigation based on the primary immunization. In addition, because Cohort 2 was changed to a design that included the period up until after the primary immunization, Cohort 3 was established so that the (sub)investigators could measure the antibody titer following the booster immunization in subjects who had completed Cohort 2, depending on the results obtained after the end of the primary immunization or the wishes of the subject (subject's legal guardian). For the Hib antigen levels of the investigational product, the results of Cohort 1, among other findings, will be judged comprehensively, and 1 dose, either the L group dose or the H group dose, will be selected and used.

It was decided that randomization will be performed to ensure the comparability of the subject populations of each of the groups, and that blinding methods (Cohort 1: Double blind; Cohort 2: Observer blind) will be used in order to minimize biases that could arise in, for example, subject selection, management, and assessment.

#### 5.2.2 Criteria for Initiating Cohort 2

Cohort 2 will be initiated if either group meets both of the following criteria.

(1) Safety

No severe and persistent adverse drug reactions or clinically intolerable adverse drug reactions that do not occur with either MT-2301 or TETRABIK are reported in Cohort 1.

(2) Hib immunogenicity

There are fewer than 2 subjects in Cohort 1 with an anti-PRP antibody concentration less than 1  $\mu\text{g}/\text{mL}$ .

Additionally, a more detailed description of the criteria for deciding to initiate Cohort 2 will be provided in separate written operating procedures.

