### 12.2 Discontinuation Procedures

If a subject is discontinued from the study during the term of the study, the (sub)investigator will take whatever actions are appropriate for the subject, and will inform the monitor in question that the subject has been discontinued from the study.

The day of study discontinuation will be the day on which the (sub)investigator made the decision to discontinue the subject from the study.

The (sub)investigator will perform follow-up by examining the subject as much as possible to investigate the presence or absence of adverse events in the 2 weeks after vaccination with the investigational product (in the period up until the day of discontinuation if the day of discontinuation is more than 2 weeks after vaccination with the investigational product). If the subject is discontinued from the study after the third or fourth dose (except for subjects discontinued in the period from after Post-vaccination Examination 1 to before the fourth vaccination), blood samples for antibody titer measurement will be collected whenever possible 4 to 6 weeks after vaccination. If a subject has not completed all of the vaccinations, the subject's legal guardian will be given a full explanation of the vaccinations that the subject will receive after the subject has been discontinued from the study.

The concomitant medications will be confirmed at discontinuation, at the time of blood sample collection (except for Cohort 3), or at 2 weeks after vaccination, whichever comes last.

The (sub)investigator will record the day of discontinuation and the reason for discontinuation\* in the case report form.

For subjects for whom the specified observations/tests cannot be performed at discontinuation, or who did not come in for any study visits after discontinuation, the reasons for this, the subject's subsequent course, etc. will be followed up either in writing (correspondence) or by telephone or the like.

If the subject does not come in for a visit, the (sub)investigator or a clinical research coordinator will ask the subject's guardian to fill out the e-Diary as much as possible.

\*: The "reason for discontinuation" will be selected from among the following.

1. Adverse event
2. Death

3. Clearly unsuitable as a subject for the study
4. Study protocol deviation
5. Technical problem
6. Subject's legal guardian requested discontinuation

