5.1. Efficacy Analysis Sets

The FAS will consist of all randomized subjects except for the following subjects.

- Subjects who did not take the investigational product at all
- Subjects for whom no antibody titer results at all could be obtained at 4 weeks after the primary immunization

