7.1.6. Tabulation Time Points and Baselines

The tabulation time points will be displayed as shown in the table below. The baseline will be "Before

the first dose at Visit 1.”

Table 7.1.5: Tabulation Time Points

Notation for Tabulation		Assessment Time Points in the Protocol
Assessment Time Point	Abbreviation	
Before the first vaccination	V1	Before the first dose at Visit 1
4 weeks after the primary immunization	V4	Post-vaccination examination at Visit 4
Before the booster immunization	V5	Before the fourth dose at Visit 5
4 weeks after the booster immunization	V6	Postdose examination 2 at Visit 6 and at discontinuation

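### Minor: Cohort 1 SAP Table 7.1.5 puts every discontinuation titer at the post-booster time point, including one taken after dose 3 from an infant who never had a booster

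*Protocol*

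**What the plan says.** The SAP file holds two plans, one for Cohort 1 and one for Cohort 2.

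- **Protocol 12.2** deals with infants who stop after dose 3 or dose 4: "blood samples for antibody titer measurement will be collected whenever possible 4 to 6 weeks after vaccination". It exempts those who stop between Post-vaccination Examination 1 and dose 4.
- **Cohort 1 SAP 7.1.6, Table 7.1.5** lists only the Visit 4 examination as the source of V4, the time point four weeks after the primary series. For V6, the time point four weeks after the booster, the source is "Postdose examination 2 at Visit 6 and at discontinuation".
- **Cohort 2 SAP 7.1.6, Table 7.1.5** adds discontinuation to the V4 row instead.
- **Cohort 1 SAP 5.1** removes from the FAS "Subjects for whom no antibody titer results at all could be obtained at 4 weeks after the primary immunization".
- **Cohort 1 SAP 6.2** uses data that fall in the visit windows of Protocol 9.1 and does not substitute data from outside them.
- **Cohort 1 SAP 7.5.1** tabulates the primary seroprotection rates in the FAS, by group, at the post-primary and post-booster time points.

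On the decision to start Cohort 2, Protocol 5.2.2 opens with "Cohort 2 will be initiated if either group meets both of the following criteria". The Hib criterion then reads "There are fewer than 2 subjects in Cohort 1 with an anti-PRP antibody concentration less than 1" µg/mL. The safety criterion concerns reactions "that do not occur with either MT-2301 or TETRABIK are reported in Cohort 1". The section adds that "a more detailed description of the criteria for deciding to initiate Cohort 2 will be provided in separate written operating procedures".

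**The concern.** An infant who stops after dose 3 and before Visit 4 can supply a valid post-primary titer. The only row of the Cohort 1 table that mentions discontinuation describes a time point this infant never reached. A programmer who follows the table finds no V4 result for the infant, and the FAS rule then removes the infant from every efficacy table.

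At stake are the Cohort 1 post-primary results: the primary seroprotection rates, the rate at 0.15 µg/mL and the geometric mean titers. With 15 infants per group, one infant visibly moves a percentage. A measured value would be lost through a label, not because the sample was missing or late.

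**Working it through.** **1. Which discontinuation titers can exist in Cohort 1.** Protocol 12.2 leaves two kinds: (A) after dose 3, from an infant who stops before Post-vaccination Examination 1; (B) after dose 4. Type B fits the V6 row. Type A is the problem.

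**2. Where each rule puts a type A titer taken 4 to 6 weeks after dose 3.**

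| Rule | Placement |
|---|---|
| Cohort 1 SAP Table 7.1.5, V4 row | Not included; Visit 4 is the only source |
| Cohort 1 SAP Table 7.1.5, V6 row | Included by name, although no booster was given |
| Cohort 1 SAP 6.2 with Protocol 9.1 | Meets the Visit 4 window (Visit 3 + 4 to 6 weeks); cannot meet the Visit 6 window (Visit 5 + 4 to 6 weeks), because there was no Visit 5 |
| Cohort 1 SAP 5.1 (FAS) | Qualifies on timing; does not qualify if the post-primary time point means V4 as Table 7.1.5 defines it |
| Cohort 2 SAP Table 7.1.5, V4 row | Included at V4 |

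Table 7.1.5 and section 6.2 of the same plan therefore give different answers, and FAS membership depends on which one is followed.

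**3. Size in the primary table.** The plan states no expected seroprotection rate, so it has no figure to reproduce. Inputs: 15 infants per group (Protocol 6.1) and two-sided 95% Clopper-Pearson intervals (SAP 7.1.3). Assumptions, for illustration only: 2 of the 15 are below 1 µg/mL, and one of those 2 is a type A infant.

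For x successes in n, the lower limit is the 0.025 quantile of Beta(x, n − x + 1) and the upper limit is the 0.975 quantile of Beta(x + 1, n − x).

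- Infant kept at V4: 13/15 = 86.7% (59.5% to 98.3%), 2 below.
- Infant dropped: 13/14 = 92.9% (66.1% to 99.8%), 1 below.

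The direction is not fixed. If the dropped infant had been at or above 1 µg/mL, the result would be 12/14 = 85.7%.

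**4. The unit in Protocol 5.2.2.** Let h and l be the numbers below 1 µg/mL in the H and L groups. Read per group, the Hib criterion is met if h < 2 or l < 2. Read pooled, it is met if h + l < 2. The readings differ exactly when h + l ≥ 2 and the smaller of h and l is 0 or 1, for example h = l = 1.

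**5. Could the label have moved the start decision?** Suppose, although no document says so, that the decision was read from the V4 table, per group, with one type A infant in one group. Let p be the true share below 1 µg/mL (assumed, since none is given), with independent groups. A group goes from 2 of 15 to 1 of 14 with probability 14p(1 − p)^13 × p. The decision changes only if the other group also has 2 or more below.

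| p | 2/15 shown as 1/14 | Other group fails | Product |
|---|---|---|---|
| 5% | 0.018 | 1 − 0.829 = 0.171 | 0.003 |
| 10% | 0.036 | 1 − 0.549 = 0.451 | 0.016 |
| 20% | 0.031 | 1 − 0.167 = 0.833 | 0.026 |

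**The case against.** The best defence is that Table 7.1.5 only sets notation and that the rest of the plan already handles the sample. The protocol's definition of terms places the post-vaccination examination 4 to 6 weeks after the third or fourth dose. SAP 6.2 admits data by window, the FAS rule names no visit, and SAP 5 leaves detailed subject handling to be settled before database lock. There may also be no such infant.

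Much of this stands. Exclusion is the literal reading of one table, not the only reading of the plan, so the point is a conflict between rules and not a certain loss of data. The table still names a source for each time point, names the wrong one for type A titers, and differs from its Cohort 2 counterpart without a stated reason.

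A reader might infer more: that the decision to start Cohort 2 rested on an undefined count, or that the visit label could have changed it. The documents do not support that. The 5.2.2 lead-in makes the group the unit; a pooled Hib count would leave the words on either group without effect. Choosing a single formulation ("1 dose, either the L group dose or the H group dose, will be selected and used") also fits a per-group reading. The detail sits in operating procedures that are not among these documents. Nothing says that SAP Table 7.5.1 must reproduce the count used for the decision, and 5.2.2 does not say whether discontinuation titers enter it. One misplaced infant matters only if the other group also fails.

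**Conclusion.** Minor, but wrong as written. Table 7.1.5 of the Cohort 1 SAP assigns a post-dose-3 discontinuation titer to a booster the infant did not receive. That conflicts with SAP 6.2, with the timing wording of the FAS rule and with the Cohort 2 SAP. The effect is limited to Cohort 1 immunogenicity tables. It is nil if nobody stopped between dose 3 and Visit 4, a number the documents do not give. The shift of about 6 percentage points (92.9 − 86.7 = 6.2) rests on the assumed case of one such infant below 1 µg/mL in a group of 15 with 2 below.

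The 5.2.2 wording is an editorial matter. The Cohort 2 SAP already names the H group (sections 2.3 and 7.1.5), so the decision has been taken, and no Cohort 2 result depends on the wording.

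**What to change.** 1. In Cohort 1 SAP Table 7.1.5, assign a discontinuation titer taken within the window after dose 3 to V4 and one taken after dose 4 to V6.
2. State in Cohort 1 SAP 5.1 that a titer so assigned to V4 counts for FAS membership.
3. Editorial: reconcile the Protocol 5.2.2 lead-in and its two criteria with the unit that the operating procedures applied. This records the rule that was used and sets no new one.

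The cost is two table cells, one sentence in the SAP and one clarifying phrase in the protocol, with no extra subjects, samples or analyses. If the Cohort 1 database is already locked, Protocol 13.4 applies: give the reason in the SAP and the study report, and keep the changed results distinct from those planned. If no infant stopped in the interval, a line in the report saying so closes the numerical question.
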